 - a. [Time frame] Self-reported abstinence and urine or saliva samples will be collected during (a) the baseline visit, (b) every week from weeks 1 to 12 during the randomization interval, and (c) at weeks 16, 20, and 24 during the follow-up interval. The primary outcome will then consist of continuous abstinence status over weeks 9, 10, 11, and 12 for each participant converted to a binary value (1 = abstinent across all 4 study visits, 0 = non-abstinent for at least one of the 4 study visits).
 - b. [Biochemical verification] Self-reported nicotine vaping abstinence will be considered verified given a semi-quantitative cotinine of less than 30ng/ml. For virtual sessions, participants will provide the sample during the videoconferencing session and will show results to the assessor. Those who report no vaping use since the last study visit but who have a cotinine of 30ng/ml or higher will be considered non-abstinent. Those who are missing cotinine values but self-report vaping will be considered non-abstinent.
 - c. [Self-reported abstinence] Self-reported vaping will be assessed at all visits using the timeline follow-back (TLFB; Robinson, Sobell, Sobell, & Leo, 2014). The recall period will be 60 days at enrollment and for all subsequent visits will be the interval between the prior and current visit.
 - d. [Randomization groups] The primary analysis will focus on V+BC and P+BC groups.

Covariates

We will use, at a minimum, 2 covariates in our analysis and missing data imputation:

- Biological sex at birth (male [referent] versus female).
- Summed scores from the ECDI (Foulds et al., 2015), a 10-item inventory with scores ranging from 0 – 20 (higher scores indicating greater E-cigarette dependence).

All covariates will be collected during the baseline visit.

Missing Data

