Missing abstinence data for any of the study weeks 9, 10, 11, or 12 will be imputed 40 times using multiple imputation via chained equations (MICE; Azur, Stuart, Frangakis, & Leaf, 2011). Abstinence status will be imputed all non-missing time points and using the set of 2 covariates collected at the baseline visit described above. Imputation will be done via fully conditional specification with predictive mean matching using logistic regression. Following each imputation iteration, the 4 observed and/or imputed values per participant across the 4 study visits will be converted into the final binary outcome via the rules given above. For instances in which a participant only partially completed the baseline ECDI, missing responses to individual questions will be singularly imputed via an item response theory model fit to all non-missing responses: a binomial regression with population-level effects for items and a participant-varying intercept term.

Statistical Model and Tests

We will use a logistic regression model to assess continuous cotinine-verified self-reported abstinence across study weeks 9 – 12 for participants in the V+BC and P+BC arms (We will exclude participants in the EUC arm). Missing data will be imputed per the method specified above. We will then apply our logistic regression model to each set of observed and imputed data, and pool the regression estimates according to Rubin's rule.

Our primary test of interest will be a dummy-coded contrast comparing the P+BC group (coded as 0) to the V+BC group (coded as 1). Statistical significance for the contrast between varenicline and placebo will be determined using a z-test applied to the pooled mean estimate divided by the pooled standard error. We hypothesize that those assigned to V+BC will have significantly higher abstinence rates compared to those assigned to P+BC, which will be confirmed with $p < 0.05$ and an odds ratio greater than one.

The logistic regression model will include the 2 covariates assessed at baseline (biological sex and summed scores for the ECDI). Covariates will be standardized (mean-centered and scaled by the standard deviation). The analysis will be intent-to-treat; all subjects randomized at the beginning of the study will be included in the analysis, irrespective of whether they receive their assigned behavioral treatment or take their assigned medication.

Secondary Outcomes

The secondary outcomes for the study will be...

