1. We will test whether our conclusion on efficacy is robust to the inclusion/exclusion of the two covariates (biological sex and nicotine dependence severity). We will rerun analyses excluding these covariates and see if conclusions change.
2. We will test whether our conclusion on efficacy is robust to the approach for imputation of missing data. We will (a) rerun the adjusted (i.e., with covariates) models on the observed data only and (b) rerun the adjusted models on a dataset with the observed data and all missing outcome data imputed as non-abstinent.
3. We will conduct a per protocol analysis by evaluating results among participants who use varenicline on most days in the trial (e.g., > 50 or 75%).

Power

Sample size was determined based on the assumption that use of varenicline for vaping cessation in adolescents would require an effect that at least doubled cessation rates over placebo to be worth the risks inherent in use of pharmacotherapy. Abstinence rates of 24% have been reported with TIQ alone in adolescents who vaped and were not necessarily dependent (Graham, Jacobs, & Amato, 2020; Graham, Amato, Cha, Jacobs, Bottcher, & Papandonatos, 2021). In this trial, requiring nicotine dependence to enroll, we postulate that addition of varenicline to behavioral counseling and TIQ will double abstinence rates. A sample size of 100 per arm, with 80 analyzable per arm, would yield power of 0.88 with a two-sided alpha of 0.05 with abstinence rates of 25% in the P+BC arm and 50% in the V+BC arm.

Software and Data Management

All analyses will be done using the statistical software R (version 4.1.1; R Core Team, 2021) and integrated development environment RStudio (version 2020.9.0.351; RStudio Team, 2021). Data will be prepared using the R packages ‘dplyr’ (version 1.0.7; Wickham, François, Henry, & Müller, 2021) and ‘tidyr’ (version 1.1.4; Wickham, 2021). Models will be fit using the R package ‘geepack’ (version 1.3-2; Højsgaard, Halekoh, & Yan, 2006). Missing data will be imputed using the R package ‘mice’ (version 3.13.0; Van Buuren & Groothuis-Oudshoorn, 2011). Reproducible code and de-identified data will be organized using the R package ‘targets’ (version 0.8.1; Landau, 2021).

References

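### Reported abstinence without a cotinine result has no scoring rule, and the listed imputation predictors omit both that visit's self-report and treatment arm

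*SAP*

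**What the plan says.** The SAP, under Primary Outcome, item b (biochemical verification), settles three situations at a visit:

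- Abstinence reported, cotinine below the cut-off: "Self-reported nicotine vaping abstinence will be considered verified given a semi-quantitative cotinine of less than 30ng/ml".
- Abstinence reported, cotinine at or above the cut-off: "Those who report no vaping use since the last study visit but who have a cotinine of 30ng/ml or higher will be considered non-abstinent".
- Vaping reported, no cotinine: "Those who are missing cotinine values but self-report vaping will be considered non-abstinent".

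A fourth situation, abstinence reported with no cotinine, is not mentioned. Item c states that "Self-reported vaping will be assessed at all visits using the timeline follow-back", so the report exists at every attended visit.

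Under Missing Data for the primary outcome, "Missing abstinence data for any of the study weeks 9, 10, 11, or 12 will be imputed 40 times". The predictors are given as follows: "Abstinence status will be imputed all non-missing time points and using the set of 2 covariates collected at the baseline visit described above". The Covariates section introduces the two covariates, sex and baseline ECDI, with "We will use, at a minimum, 2 covariates in our analysis and missing data imputation". The Secondary Outcomes section carries the same imputation to the weeks 9–24 outcome and the week 12 outcome. The two missing-data reruns under Sensitivity Analyses use observed data only, or count all missing outcomes as non-abstinent.

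**The concern.** A visit with reported abstinence and no cotinine cannot be verified, and no rule scores it as failure. The only provision left is the imputation of missing status. Among attended visits without a cotinine result, a vaping report therefore stays in the data as an observed 0, while an abstinence report drops out.

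The model that fills the gap is fitted to observed visits, which include every reported vaper but only some of the reported abstainers. As listed, it is not told that the person being imputed reported abstinence. Missingness depends on a recorded variable outside the listed model, so missing-at-random given that model fails. Status at other visits recovers part of the lost information, but not all of it.

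This affects the primary endpoint. Abstinence rates can come out too low. The V+BC versus P+BC odds ratio can move either way if cotinine gaps differ by arm. Because arm is not a listed predictor, imputed values are also pulled toward a common rate, which draws the odds ratio slightly toward 1 even when gaps are equal.

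**Working it through.** **Inputs from the SAP (Power section).** Abstinence of 25% in P+BC and 50% in V+BC; 80 analyzable per arm; power 0.88; two-sided alpha 0.05. The target odds ratio is (0.50/0.50)/(0.25/0.75) = 3.00.

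**The plan's own figure.** Pooled z-test: [0.25·√80 − 1.96·√(2·0.375·0.625)] / √(0.25·0.75 + 0.50·0.50) = (2.236 − 1.342)/0.661 = 1.352, power 0.91. With continuity correction it is 0.882, and with Fisher's exact test 0.883. The stated 0.88 is reproduced by either of the last two.

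**Assumptions not in the SAP.** The share of self-reported abstainers without cotinine is 10% to 30% per visit. The share of abstinence reports that cotinine would confirm is 90% or 98% in the simulation, and 90% or 100% in the one-visit formula.

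**One-visit formula (all reports true, no other visits to borrow from).** Let m be the gap among self-reported abstainers. The pooled observed rate with arm omitted is

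r = [0.25(1 − mP) + 0.50(1 − mV)] / [(1 − 0.25mP) + (1 − 0.50mV)],

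and each arm's completed rate is p(1 − m) + p·m·r.

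- Gaps 10%/10% (P+BC/V+BC): r = 0.675/1.925 = 0.351. Rates are 0.225 + 0.025·0.351 = 0.234 and 0.45 + 0.05·0.351 = 0.468; OR 2.88.
- Gaps 10%/30%: r = 0.575/1.825 = 0.315. Rates are 0.233 and 0.397; OR 2.17.
- Gaps 30%/10%: r = 0.625/1.875 = 0.333. Rates are 0.200 and 0.467; OR 3.50.

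With arm in the model but not the self-report, each arm's odds are multiplied by (1 − m), so OR = 3.00·(1 − mV)/(1 − mP). This gives 3.00 at equal gaps, 3.00·0.7/0.9 = 2.33 at 10%/30%, and 3.00·0.9/0.7 = 3.86 at 30%/10%. With the self-report used, the rates return to 0.25 and 0.50.

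**Four-visit simulation.** There were 20,000 per arm and four correlated visits calibrated to 25% and 50% continuous abstinence. Chained logistic imputation used the other three visits, sex and ECDI. Ranges span the 98% and 90% confirmation assumptions.

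| Gap P+BC / V+BC | Rates, listed predictors | OR, listed predictors | OR, arm added | OR, arm and self-report |
|---|---|---|---|---|
| 10% / 10% | 24.0–24.3% / 48.4–48.5% | 2.93–2.97 | 2.97–3.00 | 3.00 |
| 20% / 20% | 23.3–23.5% / 46.6–47.1% | 2.87–2.90 | 2.98–3.01 | 3.00–3.01 |
| 10% / 30% | 24.2% / 44.4–44.5% | 2.51 | 2.61 | 2.98–3.00 |
| 30% / 10% | 22.5–22.7% / 48.5% | 3.21–3.24 | 3.37–3.40 | 2.99–3.01 |

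Pooled-z power at 80 per arm, evaluated at the shifted rates and ignoring imputation variance, falls from 0.91 to 0.78 in the 10%/30% case. Adding arm alone repairs the odds ratio at equal gaps but leaves the rates low. Adding the self-report as well restores both.

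**Counter-case.** Suppose 90% of false and 10% of true abstinence reports lack cotinine, with 90% of all reports true. Per 100 reports, the unverified ones are then 10·0.9 = 9 false and 90·0.1 = 9 true, so half are false. The listed predictors give 25.4% and 50.1%, OR 2.96, and the lowering is gone. With 98% of reports true, the same gaps leave rates at 24.4% and 48.6%, OR 2.92.

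**The case against.** The quoted scoring rule is itself sound. A person who reports vaping is non-abstinent whatever the sample would have shown, whereas an unverified abstinence report leaves the status truly unknown. That stands; the defect lies in what happens next.

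A reader might infer that the SAP directs the analyst to discard the self-report. It does not. The route to imputation is by elimination, and the two covariates are described as a minimum, so more predictors are permitted. Even so, an analyst who follows the listed predictors would leave the report out.

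A reader might also infer that abstinence is understated in every arm. That needs unverified reports to be mostly true, as the counter-case shows. Compared with counting missing as non-abstinent, imputation raises the rates.

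A third tempting reading is that the primary odds ratio is badly biased. V+BC and P+BC share the same visits and counseling, with identical-looking tablets and blinded staff, so 10% versus 30% gaps between them are an assumption. Samples are given during virtual sessions, and people unwilling to give urine are excluded, which points to few gaps at attended visits. A separate simulation, with arm in the model and 8% of visits missed outright, found that 5% gaps in both arms lowered rates by 0.2 to 0.6 points and moved the odds ratio by at most about 2%. Gaps of 10% in P+BC and 5% in V+BC moved it by about 4% to 5%. All of this stands and limits the size.

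Larger gaps in EUC are also only a conjecture. EUC has weekly assessments too, was not simulated, and is outside the primary test.

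The planned reruns give some protection, but observed-only keeps the same selection and missing-as-failure pushes further the same way. Neither uses the report.

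**Conclusion.** The point holds in this form: one situation in the primary endpoint is undefined, and the imputation model as listed omits the same-visit self-report and arm. Following it can give a worse primary estimate than the collected data allow.

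At assumed equal gaps of 10%, the effect is small: rates fall by about 1 point in P+BC and 1.5 points in V+BC, and the OR is 2.93 to 2.97 against 3.00. At 10% versus 30% it becomes material, about 2.5 or 3.2 depending on which arm has the larger gap. The gap rates, the truthfulness of unverified reports and the correlation between visits are all assumptions. The simulation uses only weeks 9–12 as predictors; further time points may recover more. Neither a fixed direction of bias nor an actual imbalance between arms can be read from the SAP.

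This should be changed before analysis, because the remedy is cheap and uses data already collected.

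**What to change.** 1. State the rule for reported abstinence without cotinine: draw the cotinine result (below 30, or 30 ng/ml and above) from a model fitted to self-reported-abstinent visits, with arm, other visits' status, sex and baseline ECDI as predictors, then derive status by the existing rule.
2. Leave visits with neither report nor cotinine to the current imputation, with arm added.
3. Apply the same to the weeks 9–24 and week 12 outcomes.
4. Report cotinine gaps by arm and by self-report.
5. Keep the missing-as-non-abstinent rerun, and add a sensitivity analysis that varies the share of unverified abstinence reports taken as true.

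The cost is a few lines of SAP text and imputation code. There are two downsides. The cotinine model rests on fewer visits and may be unstable if few abstinence reports are contradicted by cotinine. It also assumes cotinine is missing at random given the report and the other predictors, so it can credit claims too readily if people who vaped withhold samples. Item 5 is there to show how much that matters.

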1. Cotinine-verified self-reported nicotine vaping abstinence from week 9 to week 24 of the study.
 - a. [Time frame] Using self-reported abstinence (see primary outcome) and biochemical verification based on urine/saliva samples (see primary outcome) collected during weeks 9, 10, 11, 12, 16, 20, and 24, the secondary outcome will consist of continuous abstinence for each participant converted to a binary value (1 = abstinent across all 7 study visits, 0 = non-abstinent for at least one of the 7 study visits).
2. Cotinine-verified self-reported nicotine vaping abstinence at week 12 of the study.
 - a. [Time frame] Using self-reported abstinence (see primary outcome) and biochemical verification based on urine/saliva samples (see primary outcome) collected during week 12, the secondary outcome will consist of 7-day point-prevalence abstinence for each participant converted to a binary value (1 = abstinent over 7 days ending at week 12, 0 = otherwise).
3. Summed scores on the Minnesota Nicotine Withdrawal Scale (MNWS; Cappelleri, Bushmakin, Baker, Merikle, Olufade, & Gilbert, 2005), a 9-item inventory with scores ranging from 0 to 36 (higher scores indicate greater severity of nicotine withdrawal).
 - a. [Time frame] The inventory will be administered at baseline, every week from weeks 1 – 12, and weeks 16, 20, and 24.
4. Summed scores on the Questionnaire of Vaping Craving (QVC; Dowd, Motschman, & Tiffany, 2019), a 10-item inventory with scores ranging from 10 to 70 (higher scores indicate greater cravings to vape).
 - a. [Time frame] The inventory will be administered at baseline, every week from weeks 1 – 12, and weeks 16, 20, and 24.
5. Summed scores on the General Distress subscale of the Mood and Anxiety Symptoms Questionnaire (MASQ-D30; Lin, Yung, Wigman, Killackey, Baksheev, & Wardenaar, 2014).
 - a. [Time frame] The inventory will be administered at enrollment, baseline and monthly during weeks 4, 8, 12, 16, 20, and 24.
6. Number of participants who report one or more adverse events as measured by the Neuropsychiatric Adverse Events Interview (NAEI; Anthenelli et al., 2016).

- a. [Time frame] The interview will be conducted at enrollment, baseline, and monthly during weeks 4, 8, 12, 16, 20, and 24.

Missing Data

Missing outcome data for the 2 vaping abstinence outcomes and the 3 inventory measures will be multiply imputed.

Biochemically-Verified Vaping Abstinence

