Missing abstinence data for any of the study weeks 9, 10, 11, 12, 16, 20, or 24 will be imputed 40 times using MICE via the same approach and covariates described for the primary outcome. Following each imputation iteration, for continuous abstinence over weeks 9 – 24, the 7 observed and/or imputed values per participant across the 7 study visits will be converted into the final binary outcome via the rules given above.

Inventory Measures

Missing summed scores for the MNWS, QVC, and the MASQ-D30 for any of the study weeks 1 – 24 will be imputed 40 times using MICE. Summed scores will be imputed using the set of 2 baseline covariates described above, as well as a participant's baseline summed score for the given inventory measure. Imputation will be done via fully conditional specification with predictive mean matching using linear regression.

Statistical Models and Tests

We will conduct 5 secondary analyses total for the 3 vaping abstinence outcomes, 3 secondary analyses and 3 exploratory analyses total for the 3 inventory measures, and a secondary analysis for adverse events.

Biochemically-Verified Vaping Abstinence

We will use a logistic regression model to assess (1) continuous vaping abstinence across study weeks 9 – 12, (2) continuous vaping abstinence across study weeks 9 – 24, and (3) 7-day point-prevalence cotinine-verified self-reported abstinence at week 12. Missing data will be imputed per the method specified above. We will then apply our logistic regression model to each set of observed and imputed data, and pool the regression estimates according to Rubin's rule.

The logistic regression model will include the 2 covariates assessed at baseline (biological sex and summed scores for the ECDI). Covariates will be standardized (mean-centered and scaled by the standard deviation). The analysis will be intent-to-treat; all subjects randomized at the beginning of the study will be included in the analysis, irrespective of whether they receive their assigned behavioral treatment or take their assigned medication.

We will conduct two types of analyses:

1. We will assess a single dummy-coded contrast comparing the P+BC group (coded as 0) to the V+BC group (coded as 1), excluding participants in the EUC group. Statistical significance will be determined using a z-test applied to the pooled mean estimate divided by the pooled standard error. We will conduct this analysis for our two secondary vaping abstinence outcomes.

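### The imputation models leave out the randomized arm, so a true varenicline effect is pulled toward no effect

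*SAP*

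**What the plan says.** The SAP's Covariates section opens: "We will use, at a minimum, 2 covariates in our analysis and missing data imputation". It then lists sex and baseline ECDI score. Primary Outcome, Missing Data, gives the abstinence imputation: "Abstinence status will be imputed all non-missing time points and using the set of 2 covariates collected at the baseline visit described above". Besides baseline and weeks 16, 20 and 24, abstinence is collected "every week from weeks 1 to 12 during the randomization interval". The primary test is of a 0/1 indicator for P+BC versus V+BC in a logistic regression, pooled over 40 imputations.

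Under Secondary Outcomes, Missing Data, abstinence missing at any visit from week 9 to week 24 "will be imputed 40 times using MICE via the same approach and covariates described for the primary outcome". For MNWS, QVC and MASQ-D30 the text reads: "Summed scores will be imputed using the set of 2 baseline covariates described above", with the participant's baseline score on the same inventory added. The method is then stated: "Imputation will be done via fully conditional specification with predictive mean matching using linear regression".

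No section names the arm as an imputation predictor, says that imputation is done separately by arm, or says which arms share one imputation.

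**The concern.** An imputation model should contain the variable whose effect the analysis will test. Here two participants in different arms with the same sex, ECDI and observed visits receive the same imputed probability of abstinence. Arm information reaches the imputed values only through a participant's own observed visits. Where those visits are few or absent, the imputed values are a blend of the arms, and the contrast shrinks.

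This touches the primary odds ratio, both secondary abstinence outcomes, the three inventory contrasts and the comparisons with EUC. Two ambiguities make the size hard to foresee. The abstinence sentence does not say whether weeks 1–8 count among the time points used. The inventory text names only baseline predictors but also specifies a fully conditional method, so it is open whether other weeks' scores enter.

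**Working it through.** **Inputs.** From the SAP, Power: 25% (P+BC) versus 50% (V+BC), 100 randomized and 80 analyzable per arm, two-sided alpha 0.05. Assumed: missing shares *m* of 5, 10, 20 and 30%, because the SAP gives no rate for weeks 9–12; missingness unrelated to arm and outcome.

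**The plan's own power figure.** With 80 per arm, the continuity-corrected test gives 0.882 and Fisher's exact test 0.883, so the stated 0.88 is reproduced and is not in question. The simulated powers below compare arm omitted with arm included only; they are not comparable with 0.88.

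**Upper bound: the missing have no post-baseline data.** Both arms' missing values are then filled at the common rate (0.50 + 0.25)/2 = 0.375:

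- V = (1 − m) × 0.50 + m × 0.375
- P = (1 − m) × 0.25 + m × 0.375

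At m = 0.20, V = 0.475 and P = 0.275, so OR = (0.475/0.525)/(0.275/0.725) = 2.39 instead of 3.00. The risk difference shrinks by the factor 1 − m, here from 25 to 20 points. Unequal missingness does not remove the dilution: 30% in one arm and 10% in the other gives OR 2.32 to 2.39.

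**Simulation of the primary analysis.** 100 per arm; 40 imputations by predictive mean matching on a logistic fit; analysis on arm, sex and ECDI; Rubin's rules; z-test; 300 trials per cell. Weekly abstinence was generated with a random intercept (SD 1.5) and a lag coefficient of 1.5, both assumed, calibrated to 25% and 50% continuous abstinence in weeks 9–12. Entries are arm omitted vs arm included.

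| Pattern | Result | 5% | 10% | 20% | 30% |
|---|---|---|---|---|---|
| Dropout spread over weeks 1–12, all weekly visits used | OR | 3.03 vs 3.09 | 2.92 vs 3.05 | 2.85 vs 3.09 | 2.72 vs 3.09 |
| | Power | 0.96 vs 0.96 | 0.93 vs 0.94 | 0.94 vs 0.95 | 0.92 vs 0.95 |
| No post-baseline data | OR, closed form (true 3.00) | 2.83 | 2.67 | 2.39 | 2.13 |
| | OR, simulated | 2.90 vs 3.06 | 2.72 vs 3.03 | 2.54 vs 3.15 | 2.15 vs 2.91 |
| | Power | 0.93 vs 0.94 | 0.91 vs 0.93 | 0.84 vs 0.94 | 0.63 vs 0.86 |

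Monte Carlo error of power is about 0.01–0.03. A large-sample run of the gradual pattern gave OR 2.95, 2.91, 2.72 and 2.63 with arm omitted, against 2.97–3.01 with arm included. With intermittent gaps only (10% of visits, 100 trials), OR was 2.93 vs 2.97 and power 0.95 in both. A second simulation with a different data model and stochastic logistic draws (250 trials, 8 imputations), at 20% with no post-baseline data, gave OR 2.48 vs 2.92 and power 0.78 vs 0.87.

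**Error rate.** In a separate run of 600 trials at 20% missing, rejection under no effect was 0.013–0.027 with arm omitted and 0.038–0.040 with arm included. The test becomes conservative: at 20–30% missing with arm omitted, the mean reported standard error is 0.334–0.353 against an empirical SD of 0.256–0.278.

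**Inventory scores.** Suppose dropout is spread evenly over weeks 1–12, the arm effect is constant and only baseline predictors are used. The arm difference is then multiplied by 1 − m × 6.5/12 for the weekly scales and by 1 − m × (4 + 8 + 12)/36 for MASQ-D30 at weeks 4, 8 and 12. At m = 0.20 these are 0.892 and 0.867. If earlier weeks' scores also enter (large-sample simulation, assumed within-person correlation 0.3 to 0.7), they become 0.94–0.96 and 0.88–0.90. If all dropout precedes week 1, the factor is 1 − m = 0.80 on either reading.

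**V+BC versus EUC.** If all three arms share one imputation and the missing have no post-baseline data, the common rate is (0.50 + 0.25 + E)/3. With E = 0.24, the rate the Power section cites for the texting program alone, this is 0.33. At m = 0.20, V = 0.466 and EUC = 0.258, so OR = 2.51 instead of 3.17. With E = 0.15 (assumed), OR = 3.88 instead of 5.67.

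**The case against.** The strongest reply is that the list is not closed. The SAP uses the word covariates for baseline adjusters only: the analysis model is described as including the same two, yet it plainly also contains the arm. The Covariates section allows additions, and the key imputation sentence is visibly incomplete. This stands in part. The plan does not forbid the arm, but it does not commit to it either, and a programmer who follows the stated predictors gets a diluted estimate.

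Second, on the plainer reading, where weeks 1–8 are used, the primary power loss is at most 0.03, within simulation error, and the large figures need every missing participant to lack post-baseline data. That is right, and those figures should be read as an upper bound. The 95% Monte Carlo error on an OR near 3 is roughly ±0.09 with 300 trials, so small differences in the table prove little alone. The large-sample run shows the pull is nevertheless real.

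Third, some rules reduce what has to be imputed: any observed vaping in weeks 9–12 settles the outcome, and self-reported vaping without a cotinine value counts as non-abstinent. The simulated chain of visits reflects the first of these but not the second.

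Fourth, the SAP plans a rerun on observed data only. Across the simulated cases this gave OR 3.00–3.22, so it would show the dilution when missingness is unrelated to arm and outcome. It remains a sensitivity analysis and does not repair the primary test. The rerun with all missing set to non-abstinent answers a different question.

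**Conclusion.** The concern holds and should be fixed. The omission and the direction of the bias are clear; the size is not, because it depends on how much is missing and when. For the primary outcome at 20% missing, the odds ratio is about 2.72 instead of 3.00 under gradual dropout with all earlier visits used. It is 2.39 if the missing have no post-baseline data. Power is nearly unaffected in the first case and falls by about 0.09 to 0.10 in the second. With intermittent gaps only, the effect is negligible. The inventory contrasts are more exposed if only baseline predictors are used, losing about 11% (weekly scales) to 13% (MASQ-D30) of the arm difference at 20% gradual dropout.

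These figures assume the SAP's 25% and 50%, missingness unrelated to arm and outcome, and the stated correlation structures. Informative dropout could add bias in either direction. Under no true effect, the omission creates no false effect.

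**What to change.** In each Missing Data section, state that the randomized arm is a predictor in every imputation model, or that imputation is run separately within arm. This should cover the primary outcome, the secondary abstinence outcomes, and the MNWS, QVC and MASQ-D30 scores, with all three arms wherever EUC is analyzed. In the same edit, say that abstinence at weeks 1–8 is a predictor of later abstinence, and that other weeks' scores of the same inventory are predictors.

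Blinding is no obstacle: the analysis model already needs an arm variable, and a masked code serves both. The cost is a sentence or two in each section and one more predictor in the code, with no new data. In the simulation the reported standard error rose by 0.000–0.011 at up to 20% missing and by 0.010–0.023 at 30%.
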